7.1.1 Cytokine Release Syndrome (CRS)

Treatment of CRS will be based on CTCAE (version 5.0) grading.

Close monitoring of fluid status by intake and output should be undertaken for the first week of blinatumomab infusion. Efforts to keep patients balanced between intake and output should be maintained, even if diuretic therapy (furosemide or similar) is needed to do this. Careful attention to fluid status may prevent deterioration from capillary leak, however even with meticulous attention some patients will experience pulmonary edema and require more aggressive respiratory support. Treating physicians should use their clinical judgment and institutional standards for whatever supportive care measures are needed during this period of time.

See Table 1 for indications to stop infusion of blinatumomab based on toxicity and CTCAE Grade.

Grade 1: Infectious work-up, initiation/escalation of antibiotics per institutional standards. IV fluids, anti-pyretic therapy as indicated with cooling blankets and acetaminophen (avoid NSAIDs). Supportive care measures.

Grade 2: Admission to hospital (if not admitted). IV fluids, infectious work-up, supportive care measures.

Grade ≥ 3 : Admission to Intensive Care Unit. Tocilizumab (8 mg/kg IV x 1; max dose 800 mg). Give a 2nd dose of tocilizumab if no response within 12-24 hours. Can give up to 2 doses of tocilizumab in 24 hours. For persistent symptoms, give solumedrol (1-2 mg/kg/day).

7.1.2 Neurologic Toxicity

Treatment of neurologic toxicity will be based on CTCAE (version 5.0) grading.

See Table 1 for indications to stop infusion of blinatumomab based on toxicity and CTCAE Grade.

Grade 1: Clinical vigilance, monitoring, supportive care

Grade 2: Admission to hospital (if not admitted), neuro-checks Q4 hours, supportive care. Dexamethasone (10 mg IV/PO every 6-12 hours; max dose 10 mg Q6 hours) can be started at discretion of provider.

Grade ≥ 3 : Admission to Intensive Care Unit. Dexamethasone 10 mg IV/PO every 6-12 hours (max dose 10 mg Q6 hours). If not improving, consider tocilizumab (8 mg/kg IV x 1; max dose 800 mg). Can give up to 2 doses of tocilizumab in 24 hours.

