4.2 Inclusion Criteria

4.2.1 Diagnosis of B-ALL in hematologic complete remission (defined as an M1 marrow, < 5% blasts) with MRD in the bone marrow ($\geq 0.01\%$) by multi-parameter flow cytometry and that meets one of the following:

- Patients in first relapse or greater;

OR

- Patients with very-high risk biology ALL that is proceeding to HCT in first remission (e.g. Induction failure, Severe-hypodiploidy, Ph-like ALL);

OR

- Patients who have persistent MRD after Consolidation therapy (End of Consolidation (EOC) MRD positive $\geq 0.01\%$);

AND with the intent of going on to an allogeneic hematopoietic cell transplantation (HCT) independent of this study

- 4.2.2 Patients must have an available donor and have intention of proceeding directly to HCT after completion of 1 to 2 cycles of Bridging therapy with blinatumomab.
- 4.2.3 Age \leq 25 years at time of study enrollment
- 4.2.4 Karnofsky Performance Status \geq 50% for patients 16 years and older and Lansky Play Score \geq 50 for patients under 16 years of age (see Appendix 1)
- 4.2.5 Have acceptable organ function as defined within 7 days of study registration:

Renal: creatinine clearance \geq 60 mL/min/1.73m² **or** serum creatinine based on age/gender as follows:

Age	Maximum Serum Creatinine (mg/dl)	
	Male	Female
1 month to < 6 months	0.4	0.4
6 months to < 1 year	0.5	0.5
1 year to < 2 years	0.6	0.6
2 years to < 6 years	0.8	0.8
6 years to < 10 years	1.0	1.0
10 years to < 13 years	1.2	1.2
13 years to < 16 years	1.5	1.4
\geq 16 years	1.7	1.4

Hepatic: ALT < 5 x upper limit of normal (ULN) and total bilirubin \leq 1.5 x upper limit of normal (ULN) for age

Cardiac: left ventricular ejection fraction \geq 40% by ECHO/MUGA

- 4.2.6 At least 7 days must have elapsed from prior chemotherapy.
- 4.2.7 Patients who have experienced their relapse after HCT are eligible, provided they have no evidence of acute or chronic Graft-versus-Host Disease (GVHD) and are off all transplant immune suppression therapy for at least 7-days (e.g. steroids, cyclosporine, tacrolimus). Steroid therapy for non-GVHD and/or non-leukemia therapy is acceptable.

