6.0 TREATMENT PLAN

6.1 Drug Administration

Up to 2 cycles of continuous infusion blinatumomab will be given based on the end of Cycle 1 disease response. Cycle 2 of blinatumomab can be given to subjects who have achieved remission (< 5% marrow blasts) after Cycle 1 but have persistent disease identified by multi-parameter flow cytometry (minimal residual disease (MRD) positive $\geq 0.01\%$) after Cycle 1. Additionally, subjects who achieved MRD negativity after Cycle 1 but are unable to proceed to HCT based on the timing/scheduling of the donor collection, a 2nd cycle of blinatumomab may be given. This additional cycle of blinatumomab for subjects awaiting donor collection, may be 28 days but can be less if the HCT is ready to proceed (e.g. 14-day blinatumomab infusion).

Minimal Organ Functions to be Met Before the Start of the Blinatumomab Infusion

Patients must meet the following criteria (prior to blinatumomab infusion)

- No oxygen requirement with oxygen saturations $> 90\%$.
- AST, ALT $< 5x$ upper limit of normal for age; bilirubin < 2 mg/dL.
- Hemoglobin > 8 mg/dL prior to infusion. (May be transfusion dependent).
- Renal function: serum creatinine $< 2 \times$ normal for age.
- Exhibit overt hematologic manifestations of relapse or persistent disease. Evidence of recurrent/persistent disease based primarily on flow cytometry, cytogenetics, chimerism analysis, or other molecular studies does not by itself represent grounds for exclusion.

Blinatumomab will be given as a 28-day continuous infusion with 14-days in between Cycle 1 and Cycle 2 as per the package insert and FDA approved labeling.

Cycle	Patient Weight Greater Than or Equal to 45kg (Fixed-dose)	Patient Weight Less Than 45kg (BSA-based dose)
1: Days 1-28	28 mcg/day	15 mcg/m ² /day (not to exceed 28 mcg/day)
Days 29-42	14-day treatment-free interval	14-day treatment-free interval
2: Days 1-28	28 mcg/day	15 mcg/m ² /day (not to exceed 28 mcg/day)
Days 29-42	14-day treatment-free interval	14-day treatment-free interval

Hospitalization is recommended for the first 3 days of Cycle 1 and the first 2 days of Cycle 2 (if needed).

Pre-medicate with prednisone or equivalent for MRD-positive B-cell Precursor ALL.

For patients \geq 18 years of age, pre-medicate with prednisone 100 mg intravenously or equivalent (e.g., dexamethasone 16 mg) 1 hour prior to the first dose of blinatumomab in each cycle.

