For pediatric patients (<18 years of age), pre-medicate with 5 mg/m² of dexamethasone, to a maximum dose of 20 mg prior to the first dose of blinatumomab in Cycle 1 and when restarting an infusion after an interruption of 4 or more hours in the first cycle.

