6.3.7 Infusion Pump Requirements

Use a programmable pump that is approved by the appropriate regulatory authority for the country in which the subject is undergoing treatment. The pump alarm must be visual and auditory. The pump must be lockable. **Elastomeric pumps are NOT allowed.** CADD pumps are allowed; however, the cassettes used in CADD pumps are not compatible with blinatumomab and thus, **not** allowed.

Record all infusion interruptions. Technical or logistical interruption must be as minimal as possible and re-start the infusion as soon as possible. If an interruption is longer than four hours, the re-start of the infusion must take place in the hospital under supervision of the investigator. Monitor patients for potential adverse events as described in the protocol and the Investigator Brochure.

Monitor patients for cytokine release syndrome, tumor lysis syndrome, and infusion reaction. Refer to protocol for specific recommendation. Monitor patients for psychiatric events such as confusion, disorientation, and cognitive attention disturbances. Patients should not drive or operate dangerous machinery while receiving blinatumomab.

Risk of Serious Adverse Reactions in Pediatric Patients Due to Benzyl Alcohol Preservative: Serious and fatal adverse reactions including “gasping syndrome” can occur in neonates and infants treated with benzyl alcohol-preserved drugs, including BLINCYTO (with preservative). The “gasping syndrome” is characterized by central nervous system depression, metabolic acidosis, and gasping respirations.

When prescribing BLINCYTO (with preservative) for pediatric patients, consider the combined daily metabolic load of benzyl alcohol from all sources including BLINCYTO (with preservative) (contains 7.4 mg of benzyl alcohol per mL) and other drugs containing benzyl alcohol. The minimum amount of benzyl alcohol at which serious adverse reactions may occur is not known.

Due to the addition of bacteriostatic saline, 7-day infusion bags of Blinatumomab solution contain benzyl alcohol and are not recommended for use in any patients weighing less than 22 kg. Prepare Blinatumomab solution for infusion with preservative-free saline in 24-hour or 48-hour infusion bags for patients weighing less than 22 kg. Please refer to Appendix 2 for infusion instructions for patients weighing less than 22 kg.

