DEX: Dexamethasone should be administered at a total daily dose of at least 0.2 - 0.4 mg/kg/day (maximum 24 mg per day) administered preferably intravenous divided 3 - 4 times daily for at least 1 day but no more than 4 days. The dose should then be stopped or tapered as clinically indicated.

SZ: Appropriate imaging should be performed to evaluate for possible hemorrhage or thrombosis, and other diagnostic procedures should be performed as clinically appropriate. Prophylactic anticonvulsant treatment with a therapeutic dose of institutional standard agents (e.g., lorazepam, phenytoin, levetiracetam) should be administered if seizures develop, and continued throughout the blinatumomab infusion. Anti-convulsant therapy should be considered starting at least 24 - 48 hours prior to any subsequent blinatumomab infusions and continuing for the remainder of those treatment cycles. Diagnostic measures to exclude potential infectious causes should be conducted once the patient has stabilized (i.e., a lumbar puncture to evaluate for bacterial, viral or fungal sources should be performed). Any identified pathology should be treated as clinically appropriate.

CNS: A daily finger-nose-finger or writing sample test is recommended according to age-appropriate activities for patients. In adults treated with blinatumomab, it has been found that a daily handwriting sample can often predict future nervous system toxicity before the clinical toxicity develops. In case of a change in finger-nose-finger or handwriting test it is recommended to start dexamethasone on the schedule above to prevent possible deterioration of nervous system toxicity. Patients who experience nervous system toxicity in the first cycle typically do not experience it again in subsequent cycles, although it is possible.

7.1 Management of Cytokine Release Syndrome (CRS), Neurologic Toxicity and Acute Graft Versus Host Disease During or Following Blinatumomab

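### Section 7.1.2 sets a flat 10 mg of dexamethasone every 6-12 hours for neurologic toxicity at any body size (2-4 mg/kg/day at 10 kg); 10 mg should be the cap on a size-scaled dose

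*Combined protocol and SAP*

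**What the plan says.** In Section 7.1.2 the Grade 2 entry reads "Dexamethasone (10 mg IV/PO every 6-12 hours; max dose 10 mg Q6 hours", and leaves it to the provider whether to start. The entry for Grade 3 or higher gives the same dose, interval and maximum, as an instruction rather than an option. Neither entry has a per-kg or per-m² term, or an age or weight threshold. The next step in the Grade 3 or higher entry is scaled and capped: "If not improving, consider tocilizumab (8 mg/kg IV x 1; max dose 800 mg".

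On who may be treated, Section 4.2.3 sets only an upper age limit of 25 years. The creatinine table in 4.2.5 begins at "1 month to < 6 months". Section 6.3.7 instructs "Prepare Blinatumomab solution for infusion with preservative-free saline in 24-hour or 48-hour infusion bags for patients weighing less than 22 kg", and Appendix 2 repeats this.

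The other systemic steroid doses are:

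- Premedication under 18 years (6.1): "pre-medicate with 5 mg/m² of dexamethasone, to a maximum dose of 20 mg".
- Premedication from 18 years (6.1): "pre-medicate with prednisone 100 mg intravenously or equivalent (e.g., dexamethasone 16 mg".
- The dexamethasone entry in the supportive-care definitions (7.0): "Dexamethasone should be administered at a total daily dose of at least 0.2 - 0.4 mg/kg/day (maximum 24 mg per day". The CNS note in the same list points to this schedule when a finger-nose-finger or handwriting test changes.
- Persistent cytokine release syndrome (7.1.1): methylprednisolone 1-2 mg/kg/day.
- Acute GVHD of Grade 2 or higher (7.1.3): prednisone 1-2.5 mg/kg/day.

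**The concern.** A single milligram dose is workable when patients are of similar size. Here they run from infants to adults of 25. A physician who follows 7.1.2 as written gives a toddler with severe neurologic toxicity the same milligrams as a grown adult. At Grade 3 or higher the amount is not worded as discretionary, and 7.1.2 offers no figure to scale to, so a physician who reduces the dose departs from the text. What is at stake is dosing safety in the smallest patients.

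**Working it through.** **Inputs.** 10 mg per dose every 6 to 12 hours (7.1.2). Comparators: 0.2-0.4 mg/kg/day dexamethasone (7.0), up to 2.5 mg/kg/day prednisone (7.1.3), and prednisone 100 mg equivalent to dexamethasone 16 mg (6.1). Of the weights, 22 kg and 45 kg are the protocol's own thresholds; 5, 10 and 70 kg are illustrations.

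**Step 1: daily dose.** Every 12 hours: 10 × 24/12 = 20 mg/day. Every 6 hours: 10 × 24/6 = 40 mg/day.

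**Step 2: dose per kg.** Divide 20 and 40 by weight, then by 0.4 mg/kg/day for comparison.

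| Weight | mg/kg/day | Relative to 0.4 mg/kg/day |
|---|---|---|
| 5 kg | 4.0-8.0 | 10-20 |
| 10 kg | 2.0-4.0 | 5-10 |
| 22 kg | 0.91-1.82 | 2.3-4.5 |
| 45 kg | 0.44-0.89 | 1.1-2.2 |
| 70 kg | 0.29-0.57 | 0.7-1.4 |

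Per kg, the 10 kg child receives 70/10 = 7 times what the 70 kg adult receives.

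**Step 3: second comparator.** 100/16 = 6.25 mg prednisone per mg dexamethasone, so 20-40 mg/day is 125-250 mg prednisone-equivalent. At 10 kg that is 12.5-25 mg/kg/day; at 70 kg it is 1.8-3.6. The top GVHD figure is 2.5. The dose is near the protocol's other steroid levels in an adult and moves away from them as weight falls.

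**Step 4: does the maximum help?** It is 10 mg every 6 hours, which is the flat dose at the shortest permitted interval. It removes nothing at any weight. By contrast, the tocilizumab cap limits a scaled dose and starts to bind at 800/8 = 100 kg.

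**Step 5: a scaled dose with 10 mg as the cap.** At 0.5 mg/kg per dose the cap binds from 10/0.5 = 20 kg, so only patients under 20 kg change. At 10 kg the dose is 5 mg, or 10-20 mg/day, which is 1-2 mg/kg/day. That is still above the 0.2-0.4 in 7.0. The per-kg excess over a 70 kg adult then never exceeds 70/20 = 3.5 times.

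**Step 6: how many patients.** The documents give no weight distribution. Footnote 2 to Table 1 gives a Grade 3 or higher neurologic toxicity rate of about 13%, not specific to this age range. Assume that rate and that 10-40% of 35 subjects weigh under 22 kg. The expected number is 35 × 0.13 × 0.10 = 0.5 to 35 × 0.13 × 0.40 = 1.8. The chance of at least one is 1 − (1 − 0.013)^35 = 37% to 1 − (1 − 0.052)^35 = 85%.

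**The case against.** The strongest reply is that no section gives a correct or maximum dexamethasone dose for established Grade 3 or higher neurologic toxicity in a child. Every comparator serves another purpose: premedication, early signs, cytokine release or GVHD. Treating severe toxicity in intensive care harder than any of these is not in itself an error. This stands. It means the ratios in the table describe how the dose drifts with size and do not measure an overdose.

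A reader might go further and infer that 7.1.2 breaches a limit in 7.0, either the 0.4 mg/kg/day or the 24 mg daily maximum. The documents do not support that. The per-kg range is worded as a minimum, and the CNS note applies the schedule to early signs. It is a comparator, not a ceiling, and the two sections are not shown to conflict.

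A second reply is that physicians will adjust, since 7.0 contains a per-kg schedule and 6.4 asks for optimal supportive care. This carries less weight. The explicit clinical-judgment sentence is in 7.1.1, on cytokine release; 6.4 is general; and the Grade 3 or higher dose in 7.1.2 is written as an instruction.

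A third is that the redundant maximum suggests a per-kg dose was dropped from the line. That is possible, but the line as it stands still doses every child at 10 mg, and the remedy is the same.

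**Conclusion.** The point holds as a gap in size scaling. Read literally, 7.1.2 gives 2-4 mg/kg/day at 10 kg and 0.91-1.82 at 22 kg, against 0.29-0.57 at 70 kg, in a trial that provides for patients this small, and its stated maximum does not limit this. It applies to Grade 3 or higher toxicity, and to Grade 2 when the provider chooses dexamethasone.

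The per-kg figures are plain arithmetic on the written dose. The right per-kg value is not in the documents. The 37-85% chance of at least one affected child rests on an assumed weight distribution and a rate not specific to this age range; it also counts children of 20-22 kg, whose dose would not change under the example in the fix. A reader might infer that harm is likely or that the trial's results are compromised; neither follows. Sample size, power and the primary analysis are unaffected. This is a cheap improvement for patient safety.

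**What to change.** In both the Grade 2 and the Grade 3 or higher lines of 7.1.2, make 10 mg the cap on a size-scaled dose, for example: *dexamethasone 0.5 mg/kg per dose (maximum 10 mg per dose) IV/PO every 6-12 hours*. The study team should confirm the per-kg value. At 0.5 mg/kg, patients of 20 kg or more keep the present dose. A much lower value needs care: 0.2 mg/kg every 12 hours is 0.4 mg/kg/day, no more than the top early-sign figure in 7.0.

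The 4-day limit from 7.0 should not be brought in with this change, because it would alter treatment at every weight. The interval range and the tocilizumab step stay as they are.

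The downside is less steroid for the smallest patients with severe toxicity, which is why the value needs clinical confirmation. The cost is one dosing line in two places and an amendment with IRB approval under 12.8; no visits, tests or subjects are added.

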7.1.3 Acute Graft Versus Host Disease (aGVHD)

Treatment of aGVHD that may flare/recur in patients includes both general supportive care of the patient and specific therapy directed at suppressing the immune process resulting in aGVHD. Specific therapy of aGVHD is based on the overall clinical grade of involvement. The grading of aGVHD is part of routine clinical care for patients receiving allogeneic blood or marrow transplants.

- 1) Patients with Grade 1 aGVHD in the setting of matched unrelated, mismatched unrelated or mismatched related donors may receive treatment of Grade 1 aGVHD at the discretion of the attending physician.
- 2) First line therapy for Grade ≥ 2 aGVHD:
 - (a) Oral prednisone 1-2.5 mg/kg/day (or equivalent methylprednisolone at the discretion of the physician).
 - (b) Topical steroids to affected areas of skin. Continue creams until one week after resolution of skin rash.
 - (c) Use other immunosuppressive medications as clinically warranted. The introduction of other second line therapies will depend on clinical severity of steroid refractory aGVHD and donor type.

8.0 ADVERSE EVENTS: DEFINITIONS AND REPORTING REQUIREMENTS

8.1 Definitions

8.1.1 Adverse Event (AE): Any unfavorable and unintended sign (including an abnormal laboratory finding), symptom, or condition temporally associated with the use of any study procedure or treatment, regardless of whether it is considered related to the study procedure or treatment. Any worsening of a pre-existing condition or illness will be considered an adverse event. The investigator will evaluate all adverse experiences as to their severity and relationship to the vaccine as well as the regimen as a whole.

8.1.2 Attribution: An assessment of the relationship between the AE and the medical intervention. CTCAE (Version 5.0) does not define an AE as necessarily “*caused by a therapeutic intervention*”. After naming and grading the event, the clinical investigator must assign an attribution to the AE using the following attribution categories:

Relationship	Attribution	Description
Unrelated to investigational agent/intervention	Unrelated	The AE is clearly NOT related to the intervention
	Unlikely	The AE is doubtfully related to the intervention
Related to investigational agent/intervention	Possible	The AE may be related to the intervention
	Probable	The AE is likely related to the intervention
	Definite	The AE is clearly related to the intervention

8.1.2.1 Relationship Assessment: In-Depth Definitions

For all collected AEs, the clinician who examines and evaluates the subject will determine the adverse event's causality based on temporal relationship and his/her clinical judgment. The degree of certainty about causality will be graded using the categories below:

- **Definitely Related:** There is clear evidence to suggest a causal relationship, and other possible contributing factors can be ruled out. The clinical event, including an abnormal laboratory test result, occurs in a plausible time relationship to drug administration and cannot be explained by concurrent disease or other drugs or chemicals. The response to withdrawal of the drug (de-challenge) should be clinically plausible. The event must be pharmacologically or phenomenologically definitive, with use of a satisfactory re-challenge procedure if necessary.
- **Probably Related:** There is evidence to suggest a causal relationship, and the influence of other factors is unlikely. The clinical event, including an abnormal laboratory test result, occurs within a reasonable time sequence to administration of the drug, is unlikely to be attributed to concurrent disease or other drugs or chemicals, and follows a clinically reasonable response on withdrawal (de-challenge). Re-challenge information is not required to fulfill this definition.
- **Possibly Related:** There is some evidence to suggest a causal relationship (e.g., the event occurred within a reasonable time after administration of the trial medication). However, the influence of other factors may have contributed to the event (e.g., the subject's clinical condition, other concomitant events). Although an adverse drug event may rate only as "possibly related" soon after discovery, it can be flagged as requiring more information and later be upgraded to "probably related" or "definitely related", as appropriate.
- **Unlikely:** A clinical event, including an abnormal laboratory test result, whose temporal relationship to drug administration makes a causal relationship improbable (e.g., the event did not occur within a reasonable time after administration of the trial medication) and in which other drugs or chemicals or underlying disease provides plausible explanations (e.g., the subject's clinical condition, other concomitant treatments).
- **Unrelated:** The AE is completely independent of study drug administration, and/or evidence exists that the event is definitely related to another etiology. There must be an alternative, definitive etiology documented by the clinician.

8.1.3 Expectedness: An AE is considered unexpected if the specificity or severity of the AE is not consistent with the protocol drug toxicity tables found in Section 8.0, or with available product information, or with the general investigational plan, or is unexpected in the professional opinion of the treating investigator.

8.1.4 Expedited Reporting: SAE reporting to the coordinating site within **five (5) calendar days** of learning of the event

8.1.5 Onset and Resolution of Adverse Events: If an adverse event occurs more than once in a course (cycle) of therapy only the most severe grade of the event should be reported.

- If an adverse event progresses through several grades during one course of therapy, only the most severe grade should be reported.
- The duration of the AE is defined as the duration of the highest (most severe) grade of the Adverse Effects.
- The resolution date of the AE is defined as the date at which the AE returns to baseline

or less than Grade 1, whichever level is higher (note that the resolution date may therefore be different from the date at which the grade of the AE decreased from its highest grade). If the AE does not return to baseline the resolution date should be recorded as "ongoing."

- An adverse event that persists from one course to another should only be reported once unless the grade becomes more severe in a subsequent course. An adverse event which resolves and then recurs during a different course, must be reported each course it recurs.

8.1.6 Protocol Therapy: Any of the study interventions (drugs) administered as part of this study.

8.1.7 Serious Adverse Event (SAE): An adverse event that results in any of the following outcomes:

Death of Patient: An event that results in the death of a patient.

Life-Threatening: An event that, in the opinion of the investigator, would have resulted in immediate fatality if medical intervention had not been taken. This does not include an event that would have been fatal if it had occurred in a more severe form.

Hospitalization: An event that results in an admission to the hospital for any length of time. This does not include an emergency room visit or admission to an outpatient facility. Additionally, any hospitalization for the purpose of treatment as per the protocol or any standard of care treatment will not be considered an SAE.

Prolongation of Hospitalization: An event that occurs while the study patient is hospitalized and prolongs the patient's hospital stay.

Congenital Anomaly: An anomaly detected at or after birth, or any anomaly that results in fetal loss.

Persistent or Significant Disability/Incapacity: An event that results in a condition that substantially interferes with the activities of daily living of a study patient. Disability is not intended to include experiences of relatively minor medical significance such as headache, nausea, vomiting, diarrhea, influenza, or accidental trauma (e.g., sprained ankle).

Important Medical Event Requiring Medical or Surgical Intervention to Prevent Serious Outcome: An important medical event that may not be immediately life-threatening or result in death or hospitalization, but based on medical judgment may jeopardize the patient and may require medical or surgical intervention to prevent any of the outcomes listed above (i.e., death of patient, life-threatening, hospitalization, prolongation of hospitalization, congenital anomaly, or persistent or significant disability/incapacity). Examples of such events include allergic bronchospasm requiring intensive treatment in an emergency room or at home, blood dyscrasias or convulsions that do not result in inpatient hospitalization, or the development of drug dependency or drug abuse.

8.1.8 Routine Reporting: AE reporting to the coordinating site at the time of the regularly scheduled time points listed in the Case Report Forms (CRFs).

